10.6. Algorithm for RESCUE TREATMENTS

1. Not required to adjudicate rescue treatment:

Post-baseline medications (WHODD-coded) given for indications consistent with AD ¹

a. Always considered rescue:

- ATC2 = CORTICOSTEROIDS FOR SYSTEMIC USE
- ATC2 = IMMUNOSUPPRESSANTS
- Preferred Drug Name = Ciclosporin
- Preferred Drug Name = Methotrexate
- Preferred Drug Name = Mycophenolate sodium
- Preferred Drug Name = Mycophenolic acid
- Preferred Drug Name = Mycophenolate mofetil
- Preferred Drug Name = Azathioprine

b. Never considered rescue

- ATC2 = EMOLLIENTS AND PROTECTIVES
- ATC2 = VASOPROTECTIVES
- ATC2 = ANALGESICS
- ATC2 = ANTI-ACNE PREPARATIONS
- ATC2 = TOPICAL PRODUCTS FOR JOINT AND MUSCULAR PAIN
- ATC2 = ANTIBIOTICS AND CHEMOTHERAPEUTICS FOR DERMATOLOGICAL USE
- ATC2 = ANTIVIRALS FOR SYSTEMIC USE
- ATC2 = ANTIFUNGALS FOR DERMATOLOGICAL USE
- ATC2 = ANTISEPTICS AND DISINFECTANTS
- ATC2 = ANTIHISTAMINES FOR SYSTEMIC USE
- ATC2 = ANTIPRURITICS, INCL. ANTIHISTAMINES, ANESTHETICS, ETC.
- ATC2 = GENERAL NUTRIENTS
- ATC2 = VITAMINS
- ATC2 = DRUGS FOR OBSTRUCTIVE AIRWAY DISEASES
- ATC2 = OPHTHALMOLOGICALS
- ATC2 = ANTIINFLAMMATORY AND ANTIRHEUMATIC PRODUCTS
- ATC2 = PSYCHOLEPTICS
- ATC4 = CORTICOSTEROIDS, WEAK (GROUP I)

- ATC1 = ANTIINFECTIVES FOR SYSTEMIC USE
- ATC1 = BLOOD AND BLOOD FORMING ORGANS
- ATC1 = ALIMENTARY TRACT AND METABOLISM
- ATC1 = MUSCULO-SKELETAL SYSTEM
- ATC2 = COUGH AND COLD PREPARATIONS
- Preferred Drug Name = TRIAMCINOLONE ACETONIDE

¹ A blinded review of all post-baseline medications to adjudicate rescue treatment, based on medical judgement, may be performed in addition. A listing of treatments classified as rescue/non-rescue in a manner inconsistent with the classification under #1 will be provided, along with supporting rationale.

1. Require to adjudicate rescue treatment

- All other medications (not noted in 1. above) given for indications consistent with AD²
- Medications noted in 1a above, when given for indications not consistent with AD

² Below is a list of indications consistent with AD based on PT level from concomitant medication/procedure data using MedDRA dictionary

System Organ Class	High Level Term	Preferred Term	Preferred Term Code
Infections and infestations	Bacterial infections NEC	Eczema impetiginous	10051890
Infections and infestations	Skin structures and soft tissue infections	Dermatitis infected	10012470
Infections and infestations	Skin structures and soft tissue infections	Eczema infected	10014199
Skin and subcutaneous tissue disorders	Dermatitis and eczema	Dermatitis	10012431
Skin and subcutaneous tissue disorders	Dermatitis and eczema	Dermatitis atopic	10012438
Skin and subcutaneous tissue disorders	Dermatitis and eczema	Eczema	10014184
Skin and subcutaneous tissue disorders	Dermatitis and eczema	Neurodermatitis	10029263

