Rescue treatments (i.e. both medications and procedures): If medically necessary (i.e. to control intolerable AD symptoms), rescue treatment for AD may be provided to study patients at the discretion of the investigator. Investigators will be required to perform an IGA assessment prior to starting rescue treatment and initiate rescue treatment only in patients who either have an IGA score = 4 or have intolerable symptoms. If possible, investigators are encouraged to consider rescue initially with topical treatment (e.g., high potency TCS) and to escalate to systemic medications only for patients who do not respond adequately after at least 7 days of topical treatment. Patients may continue study treatment if rescue consists of topical medications.

Patients who receive systemic corticosteroids or systemic non-steroidal immunosuppressive drugs (e.g., cyclosporine, methotrexate, mycophenolate-mofetil, azathioprine, etc.) as rescue medication during the study will be discontinued permanently from the study drug. All patients will be asked to complete the scheduled study visits and assessments whether or not they complete study treatment and whether or not they receive rescue treatment for AD. Investigators should make every attempt to conduct efficacy and safety assessments (e.g., disease severity scores, safety laboratory tests) immediately before administering any rescue treatment. An unscheduled visit may be used for this purpose, if necessary. For the purpose of efficacy analysis, patients who receive rescue treatment during the study will be considered treatment failures.

Blinded adjudication of rescue treatments will be implemented before database locks by considering the type of medication or procedure, indication, timing, frequency and the potential impact of the use of the prohibited medication or procedure. The rescue treatments will be adjudicated by the clinical study director and the adjudication procedure will be documented.

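### SAP 10.6 does not require rescue adjudication for a high-potency topical steroid recorded under a symptom term such as Pruritus

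*SAP*

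**What the plan says.** SAP 4.3 defines rescue as covering medications and procedures and makes adjudication a commitment: "Blinded adjudication of rescue treatments will be implemented before database locks by considering the type of medication or procedure, indication, timing, frequency". The sentence goes on to name the potential impact of the prohibited medication or procedure. SAP 4.3 and Protocol 7.3 both encourage topical treatment, with high-potency TCS as the example, as the first rescue step.

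SAP 10.6 turns this into lists.

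- **Item 1**, headed "Not required to adjudicate rescue treatment", covers medications given for AD-consistent indications. List 1a (always rescue) holds systemic corticosteroids, "ATC2 = IMMUNOSUPPRESSANTS" and named systemic drugs. List 1b is never rescue.
- **The item on required adjudication** has two bullets: "All other medications (not noted in 1. above) given for indications consistent with AD" and "Medications noted in 1a above, when given for indications not consistent with AD".
- **Footnote 2** defines the indications: "Below is a list of indications consistent with AD based on PT level from concomitant medication/procedure data using MedDRA dictionary". It has seven terms, from Eczema impetiginous to "Neurodermatitis". None is a symptom term.
- **Footnote 1** adds a wider check, but only as an option: "A blinded review of all post-baseline medications to adjudicate rescue treatment, based on medical judgement, may be performed in addition".

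SAP 5.7.1 counts a patient as a non-responder from the time of rescue. Its heading speaks of adjudicated rescue treatment, and it refers to Section 4.3.

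**The concern.** Under 10.6 a drug outside list 1a becomes rescue only through adjudication, so the entry gate matters. A site that treats intolerable itch may enter the symptom instead of the disease. Two children given the same high-potency TCS could then differ on the primary endpoint because one record says eczema and the other says pruritus. The same status decides which data are set to missing for the continuous endpoints (SAP 5.7.2) and in the LOCF sensitivity analysis.

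The second bullet shows that the authors foresaw off-list indications for list 1a agents. The topical step that investigators are asked to try first has no equivalent bullet. Both bullets also speak of medications only, so phototherapy has no stated mandatory route in 10.6, although 4.3 covers procedures.

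**Working it through.** **Routing.** Applying the 10.6 text to four records:

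| Record | Bullet 1 | Bullet 2 | Result |
|---|---|---|---|
| High-potency TCS, AD term | met | not met | adjudication required |
| High-potency TCS, Pruritus | not met: term not among the seven | not met: drug not in 1a | not required |
| List 1a agent, AD term | – | – | automatic rescue |
| List 1a agent, Pruritus | not met | met | adjudication required |

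That high-potency TCS lies outside 1a is read from the class names, because the documents give no ATC codes for individual products. SAP 4.3 lets one medication carry several ATC links, so a product with a second, systemic link would be caught by bullet 2. For topical calcineurin inhibitors (TCI), the answer depends on whether coding links them to the immunosuppressant class.

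**Size.** Inputs from the documents: 110 patients per arm in the FAS (Protocol 10.2, SAP 2.2); planned IGA 0/1 rates of 5% placebo, 22% Q4W and 28% Q2W; planned EASI-75 rates of 17%, 62% and 68%.

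Assumptions, none from the documents: 10–40% of placebo and 5–20% of dupilumab patients rescued; 5–20% of those recorded only under a symptom term and missed; response among the missed equal to the planned rate.

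Expected misclassified responders = 110 × rescued share × missed share × response rate.

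- IGA, placebo: 110 × 0.10 × 0.05 × 0.05 = 0.03, up to 110 × 0.40 × 0.20 × 0.05 = 0.44
- IGA, Q4W: 110 × 0.05 × 0.05 × 0.22 = 0.06, up to 110 × 0.20 × 0.20 × 0.22 = 0.97
- IGA, Q2W: the same with 0.28 = 0.08 to 1.23
- EASI-75: placebo 0.09 to 1.50, Q4W 0.17 to 2.73, Q2W 0.19 to 2.99

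**Power for the Q4W IGA comparison**, the least powered. The plan states 87% at 80 per group. With pooled variance, power = Φ[(d − 1.96·SE0)/SE1], where SE0 = √(2p̄(1−p̄)/n) and SE1 = √((p0(1−p0)+p1(1−p1))/n). This gives 89.0% at 80 per group. A Fisher exact calculation gives 87.2%, so the plan's figure reproduces.

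At 110 per arm:

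- No misclassification, 22% v 5%: (0.170 − 1.96 × 0.0461)/0.0446 = 1.79, power 96.3%.
- Placebo maximum, 0.44/110 = 0.4 points, 22% v 5.4%: (0.166 − 1.96 × 0.0464)/0.0450 = 1.67, power about 95.3%.
- One whole extra placebo responder, 1/110 = 0.9 points, 22% v 5.9%: 93.6%. This exceeds the assumed placebo maximum and serves only as a yardstick.

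For EASI-75, 2.99/110 = 2.7 points at most, against planned differences of 45 and 51. Power stays above 99.9%.

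**Direction.** Missed rescue on placebo raises the placebo rate and shrinks the difference. Missed rescue on dupilumab inflates it. The documents do not show which would dominate.

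**The case against.** The strongest reply is that 4.3 governs. SAP 5.7.1 points to 4.3, not 10.6, and 4.3 already mandates a documented blinded adjudication of medications and procedures. Rescue there means treatment for AD, and Protocol 7.2 directs high-potency TCS at persisting or worsening lesions, so an AD term is the usual entry. There are further safeguards:

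- Sensitivity analysis 2 in SAP 5.7.1 uses observed data whatever the rescue status.
- SAP 10.3 lists high-potency TCS outside rescue, TCI, crisaborole and phototherapy as potential major violations with no indication limit, so the per-protocol set is a partial backstop. That list is preliminary.
- Type and potency of TCS are recorded at clinic visits and tubes are weighed (Protocol 8.2.2.17), so use would be visible, though this does not set rescue status.

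All of this stands and keeps the point small. It does not close the gap, because the record-level instructions are in 10.6 and the review that would reach the record is optional.

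A reader might infer three stronger things that the documents do not support.

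1. **That 10.6 contradicts 4.3.** SAP 4.3 sets no record-level trigger. The difference is that indication is weighed in one place and used as a gate in the other. Nor does 10.6 declare the disputed record non-rescue.
2. **That crisaborole is permitted rescue slipping through.** It is prohibited and never named as permitted rescue. Under Protocol 7.4.2.1, prohibited medication leads to permanent discontinuation of study drug.
3. **That power is at risk.** A five-point rise in placebo IGA response would cut Q4W power to about 68%, but it needs 5.5 extra responders. At the largest assumed number missed, 110 × 0.40 × 0.20 = 8.8 children, 5.5/8.8 = 62.5% of them would have to reach IGA 0/1, against a planned 5%.

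**Conclusion.** The gap is real in the text of 10.6. For a drug outside list 1a, a closed list of seven terms decides whether adjudication is required, and a high-potency TCS recorded under a symptom term falls outside it. The rule feeds the primary endpoint, so this is more than missing detail.

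The effect is minor: about 0 to 1 IGA responders per arm and at most about 3 EASI-75 responders. The rescue, recording and response rates behind these figures are assumed, and the counts scale in proportion to them. The response rate could be too high, since these children had IGA 4 or intolerable symptoms, or too low if the rescue worked. Doubling the placebo IGA rate to 10% gives at most 110 × 0.40 × 0.20 × 0.10 = 0.88 responders. What is at stake is consistent classification, not the trial's conclusion.

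**What to change.** Before database lock, add a third bullet to the required-adjudication item of SAP 10.6. Every post-baseline record of high-potency or stronger TCS, TCI, crisaborole or phototherapy goes to the blinded adjudication planned in 4.3, whatever its coded indication. Change the wording of that item to cover medications and procedures. This mirrors what the second bullet does for list 1a agents and changes no treatment rule.

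Do not add Pruritus to footnote 2. That list also defines item 1, so list 1a drugs given for itch would move from required adjudication to automatic rescue.

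The cost is a few lines of text, plus the adjudicator's time to review and dismiss a few non-AD uses.

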10.7. PROMIS Scoring Tables

Anxiety 8a - Pediatric v2.0		
Short Form Conversion Table		
Raw Score	T-Score	SE*
8	33.5	5.9
9	38.0	4.9
10	40.6	4.7
11	43.0	4.4
12	44.9	4.2
13	46.7	4.0
14	48.3	3.9
15	49.8	3.8
16	51.2	3.8
17	52.5	3.7
18	53.8	3.7
19	55.1	3.7
20	56.3	3.7
21	57.5	3.7
22	58.7	3.7
23	59.9	3.7
24	61.0	3.7
25	62.2	3.7
26	63.4	3.7
27	64.5	3.7
28	65.7	3.6
29	66.9	3.6
30	68.1	3.6
31	69.3	3.7
32	70.6	3.7
33	71.8	3.7
34	73.2	3.7
35	74.6	3.8
36	76.0	3.8
37	77.6	3.9
38	79.3	4.0
39	81.1	3.9
40	83.3	3.8

SE* = Standard Error on T-Score

Pediatric v2.0 - Depressive Symptoms 8a		
Short Form Conversion Table		
Raw Score	T-Score	SE*
6	36.2	5.9
7	42.1	4.4
8	45.4	4.0
9	48.0	3.6
10	50.2	3.4
11	52.1	3.3
12	53.9	3.2
13	55.6	3.1
14	57.2	3.1
15	58.9	3.1
16	60.5	3.1
17	62.1	3.1
18	63.7	3.1
19	65.3	3.1
20	66.8	3.1
21	68.4	3.1
22	70.0	3.1
23	71.5	3.0
24	73.1	3.0
25	74.7	3.0
26	76.3	3.1
27	78.1	3.2
28	80.2	3.3
29	82.5	3.4
30	84.7	3.2

SE* = Standard Error on T-Score

Signature Page for VV-RIM-00078151 v2.0

ESig Approval	 gement 10-May-2019 14:29:14 GMT+0000
---------------	-------------------------------------------------------------------------------------------------------------------------------

ESig Approval	 10-May-2019 14:33:46 GMT+0000
---------------	---------------------------------------------------------------------------------------------------------------------

ESig Approval	 ment 10-May-2019 16:24:17 GMT+0000
---------------	-----------------------------------------------------------------------------------------------------------------------------

Signature Page for VV-RIM-00078151 v2.0 Approved
